Fructosamine			X				X			X			X			X	X
1,5-anhydroglucitol			X				X			X			X			X	X
Serum PK Samples				X ^g	X ^h	X	X	X	X	X		X	X		X	X	X
Serum Anti-PF-06293620 Antibodies Samples (ADA)			X							X			X			X	X ^d
Banked biospecimens			X														
Cardiac Telemetry			X	X	X												
Randomization			X														
Administer Study Drug				X													

Injection site assessment/infusion reaction assessment ^h			X	X			X									
Metformin compliance ⁱ			X						X			X			X	X
Prior/Concomitant Medications	X	X	X	X	X	X	X	X	X		X	X		X	X	X
Contraception check ^m	X															
Adverse Event Monitoring		X	X	X	X	X	X	X	X	X	X	X		X	X	X

- a. Weight measure in gown, undergarments and socks while fasting and empty bladder. Height measured with wall-mounted stadiometer at screening only in stocking feet and carried forward.
- b. Vital signs: blood pressure, pulse, temperature. Only blood pressure should be collected in triplicate. On Day 1 obtain vital signs prior to dose and at 1, 2, 4, 8 and 12 hours after dosing.
- c. Screening labs include FSH in women only, TSH, C-peptide, HIV, hepatitis B surface antigen, hepatitis B core antibody, hepatitis C antibody.
- d. Subjects will continue to be monitored beyond the last scheduled visit, if necessary, for elevated glucagon or ADA levels (at approximately 1-3 month intervals) until their glucagon/ADA levels return to approximate baseline or establish a new steady-state level.
- e. Samples for MMTT assessment should be collected prior to the MMTT (0 minutes/fasting) and after the start of the liquid meal at 15, 30, 60, 120, 180 and 240 minutes. Blood glucose, C-peptide, insulin, glucagon and GLP-1 will be measured at all timepoints.
- f. Fingersticks with glucometer measurements to be taken before breakfast (fasting), 2-hr post-breakfast, before lunch, 2-hr post-lunch, before dinner, 2-hr post-dinner, prior to snack (between 9 and 10 pm) at 0300 and before breakfast (fasting) the following day (Day 2, Day 5 Day 16 & Day 30). Day 16 and Day 30 are performed by the subject at home, no clinic visit required.
- g. PK Day 1: sample at hours 0 (predose), 1, 4, 8, and 12 hours after dosing.
- h. Perform injection site assessment immediately after injection, 15 minutes, 30 minutes, 1 hour, and 2 hours post administration. Additional assessments should be performed as needed after the last assessment of 2 hrs post-dose on Day 1.
- i. Subject to be questioned about compliance with metformin.

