6.3.5. Day 2 - MAD

On Day 2, after an overnight fast of at least 10 hours, the following procedures will be completed:

- Assess symptoms by spontaneous reporting of adverse events and by asking the subjects to respond to a non-leading question such as “How do you feel?”
- Assess patency of peripheral IV (PIV)/heplock, in accordance with site policies,

- If no longer patent remove and insert a new PIV/heplock in accordance with site policies. Allow subject to rest at least 1 hour prior to obtaining vital signs.
- Complete 24 hour continuous blood pressure monitoring.
 - NOTE: Before proceeding with any other Day 2 assessments, immediately upload the ABPM data to the vendor to determine if the data passes vendor QC. If the data fails technical QC, immediately restart/repeat the ABPM on Day 2 to ensure a complete dataset is obtained. Then start the remaining Day 2 procedures. If the 24 hour ambulatory blood pressure monitoring cannot be repeated on Day 2 please contact the sponsor to discuss alternative times.
- Conduct full physical exam.
- Obtain fasting weight.
- Collect blood sample for pharmacokinetic analysis at 24 hours after Day 1 dosing.
- Collect blood samples for FPG and fasting glucagon.
- Collect fasting blood and urine samples for safety laboratory tests 24 hours after Day 1 dosing.
- Obtain triplicate 12-lead ECG measurements 24 hours after Day 1 dosing.
- Assess temperature, supine pulse and triplicate supine blood pressure 24 hours after Day 1 dosing. Blood pressure is the only vital sign to be collected in triplicate.
- Assess injection site for reactions if necessary (required if a reaction was observed on Day 1).
- Record concomitant medications.
- Question subject on metformin compliance.

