7.2. Safety

7.2.1. Laboratory Tests

The following safety laboratory tests will be performed at times defined in the [Study Procedures](#) section of this protocol. Additional laboratory results may be reported on these samples as a result of the method of analysis or the type of analyzer used by the clinical laboratory; or as derived from calculated values. These additional tests would not require additional collection of blood. Unscheduled clinical labs may be obtained at any time during the study to assess any perceived safety concerns.

A central lab vendor will be used to analyze the tests to ensure accuracy and consistency in test results. The vendor will transmit all results for protocol tests, scheduled and unscheduled, to the sponsor for inclusion in the clinical database. Urinalysis will be performed on mid-stream, clean catch specimens.

Table 9. Laboratory Tests

Hematology	Chemistry	Urinalysis	Other
Hemoglobin	BUN/urea and Creatinine	pH	Apo B
Hematocrit	Glucose (fasting)	Glucose (qual)	FSH ^b
RBC count	Calcium	Protein (qual)	Urine drug screen ^c
MCV	Sodium	Blood (qual)	HIV
MCH	Potassium	Ketones	Hepatitis Screen
MCHC	Chloride	Nitrites	
 • Hepatitis B Surface Ag • Hepatitis B Core Ab • Hepatitis C Ab
Platelet count	Total CO ₂ (Bicarbonate)	Leukocyte esterase	Amylase
WBC count	AST, ALT	Urobilinogen	Lipase
Total neutrophils (Abs)	GGT ^e	Urine bilirubin	HbA1c
Eosinophils (Abs)	LDH ^e	Microscopy ^a	Fasting lipid profile (total cholesterol, LDL-C, HDL-C, non-HDL-C, triglycerides)\
Monocytes (Abs)	Total bilirubin		TSH
Basophils (Abs)	Indirect bilirubin		PK
Lymphocytes (Abs)	Direct bilirubin		ADA
	Alkaline phosphatase		Fructosamine
	Uric acid		1, 5-anhydroglucitol
	Albumin		
	Total protein		
	Creatine kinase		
Coagulation	Additional Tests ^d		MMTT
(aPTT/PT/INR)	AST, ALT (repeat) Total bilirubin (repeat) Albumin (repeat) Alkaline phosphatase (repeat) Direct bilirubin (repeat) Indirect bilirubin (repeat) GGT (repeat)		Fasting Plasma Glucose Fasting GLP-1 Fasting Glucagon C-Peptide Insulin

^a Only if urine dipstick is positive for blood, protein, nitrites or leukocyte esterase.

^b At Screening only, in women only

^c At Screening and Day -2 (SAD only) and Day -3 (MAD only).

^d Additional testing for potential Hy's Law cases only

^e GGT and LDH: SAD Cohorts: will be performed in subjects with ALT and/or AST $\geq 3 \times \text{ULN}$; MAD Cohorts: will be performed in all subjects

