7.2.12. Injection Site Reaction Evaluation

Assessments made of the injection sites in the abdominal fat fold to monitor local tolerability to PF- 06293620 subcutaneous injections will be performed up to at least 2 hours following study drug administration at times specified in the [Schedule of Activities](#) section of this protocol. Site tolerability assessments should continue after each dosing day visit, only if injection site pain or ISR characteristics continue to persist. The assessments should continue at regularly scheduled visits until the symptoms resolve. Additional assessments should be performed as needed after the last assessment of 2 hrs post-dose on Day 1.

The injection sites will be assessed for erythema, induration, ecchymosis, injection site pain, injection site pruritus, or other observed characteristics after investigational product administration. The diameter of the affected area will be measured and the condition of the injection site will be recorded in the Subcutaneous Injection Site Assessment CRF. Any observed abnormality at the injection site will be judged by the investigator to determine whether a corresponding AE should be reported. Injection site reactions should be immediately photographed in color, with a scaled ruler placed by the reaction, and these photographs should be included in the subject's source documentation. Dermatologic photos will be redacted/remove any personal identifying information and will only contain the subject study ID. When appropriate, at the discretion of the investigator, a subject with an ISR may be referred for a dermatological consultation and a skin biopsy may be obtained for further histological examination of the ISR.

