9. HANDLING OF MISSING VALUES

Missing values will not be imputed.

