10. STATISTICAL METHODOLOGY AND STATISTICAL ANALYSES

10.1. Statistical Methods

- All analyses will be presented by dose group.
- Placebo subjects will be pooled across cohorts for analysis and presentation purpose.
- Continuous data will be summarized using descriptive statistics: number of subjects (n), mean, standard deviation, standard error, median, minimum and maximum. 90% confidence intervals (CI) may be provided for pharmacodynamics endpoints.
- Categorical data will be described using frequencies and percentages. The denominator for all percentages will be the number of subjects for whom there are data in the cohort/treatment group within the analysis set of interest, unless otherwise specified. Counts of subjects with missing data will be presented if applicable.
- All data will be presented in listings. Data that will only be listed (not summarized) are specified in the analysis section.

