10.2.2.6. Injection Site Reaction Evaluation

The injection sites were assessed for erythema, induration, ecchymosis, injection site pain, injection site pruritus, or other observed characteristics after investigational product administration. Injection site reaction evaluation will be summarized by dose and reaction response over time.

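### Injection-site reaction percentages after the 2-hour check would be taken mainly among subjects who had already reacted, because the SAP divides by subjects with data

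*SAP*

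**What the plan says.** **Examined in everyone.** On SC dosing days the schedule footnotes for both parts of the study read: "Perform injection site assessment immediately after injection, 15 minutes, 30 minutes, 1 hour, and 2 hours post administration". In MAD this is repeated on Days 29 and 57 (Protocol 6.3.13 and 6.3.16).

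**Examined depending on outcome.** For MAD Day 2, Protocol 6.3.5 says: "Assess injection site for reactions if necessary (required if a reaction was observed on Day 1". Protocol 6.2.4 and 6.2.7 set the same trigger for SAD Days 2 and 5. Protocol 7.2.12 adds that, after a dosing-day visit, assessments continue "only if injection site pain or ISR characteristics continue to persist".

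**Analysis.** SAP 10.2.2.6 says: "Injection site reaction evaluation will be summarized by dose and reaction response over time". It names no denominator. The general rule in SAP 10.1 therefore applies: frequencies and percentages for categorical data, where "The denominator for all percentages will be the number of subjects for whom there are data in the cohort/treatment group", unless something else is specified. SAP 9 states: "Missing values will not be imputed". SAP 10.1 also says: "Counts of subjects with missing data will be presented if applicable".

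**The concern.** After 2 hours, whether a site is examined depends on whether it had already reacted. A percentage over subjects with data then estimates how often reactions persist among reactors. A reader of a by-dose, over-time table will take it as the proportion of dosed subjects with a reaction. Because nothing is imputed, a subject whose site was clear and therefore not re-examined drops out of the denominator and is not counted as reaction-free.

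Tolerability of SC dosing is part of the primary objective of this first-in-human study, and this table is its direct local-tolerability display. If the later cells rest on reactors only, they overstate how common reactions are. Each dose group also has its own self-selected denominator. A placebo group with no reactors may have no denominator at all.

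**Working it through.** The documents give no injection-site reaction rate, so there is no stated figure to reproduce. The reaction counts below are assumptions.

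**Inputs**
- n, active subjects dosed: 6 per SAD cohort (SAP Table 1); 8, 16 and 8 at 50, 75 and 150 mg in MAD (SAP Table 2).
- Pooled MAD placebo: 2 + 4 + 2 = 8 (SAP Table 2, pooled under SAP 10.1).
- k, reactors on Day 1: assumed 1 to 3.
- s, reactors still reacting on Day 2: assumed 0 to k.

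**Formulas, if exactly the k reactors are examined on Day 2**
- Day 1 rate = k/n
- Day 2 rate under SAP 10.1 = s/k
- Day 2 rate over all dosed = s/n, with unexamined sites taken as clear
- Ratio of the two Day 2 rates, for s of at least 1 = (s/k)/(s/n) = n/k
- The reported rate rises above Day 1 only if s/k > k/n

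| n | k | s | Day 1 | Day 2, SAP rule | Day 2, all dosed | Ratio | Rises? |
|---|---|---|---|---|---|---|---|
| 6 | 1 | 1 | 16.7% | 100% | 16.7% | 6 | yes |
| 8 | 2 | 1 | 25% | 50% | 12.5% | 4 | yes |
| 8 | 3 | 1 | 37.5% | 33.3% | 12.5% | 2.67 | no |
| 8 | 2 | 0 | 25% | 0% | 0% | n/a | no |
| 16 | 2 | 1 | 12.5% | 50% | 6.25% | 8 | yes |
| 16 | 3 | 2 | 18.75% | 66.7% | 12.5% | 5.33 | yes |

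For k from 1 to 3, the ratio n/k runs from 2 to 6 at n = 6, from 2.67 to 8 at n = 8, and from 5.33 to 16 at n = 16.

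**How often the reported rate rises.** Take n = 8, an assumed 20% Day 1 rate and at least one reactor. The chance that the Day 2 figure exceeds the Day 1 figure is 0.11, 0.29, 0.57 and 0.83 when each reaction persists with probability 10%, 25%, 50% and 75%.

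**Comparisons between groups.** Take two groups of 8, each with one subject still reacting on Day 2. With k = 1 the table shows 1/1 = 100%; with k = 2 it shows 1/2 = 50%. Both are 1/8 = 12.5% of those dosed, and the group with fewer Day 1 reactions looks worse. If none of the 8 pooled MAD placebo subjects reacts and none is re-examined, the placebo cell is empty, where 0/8 = 0% is the comparator wanted.

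**If some non-reactors are also examined.** With m extra subjects examined and found clear, the rate is s/(k + m) and the inflation n/(k + m). For n = 8, k = 2, s = 1, m = 2 this gives 1/4 = 25%, a ratio of 2. With all examined (m = n − k) the ratio is 1 and the problem is gone.

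**If the all-dosed figure is too low.** It assumes no late-onset reaction at an unexamined site. For n = 8, k = 2, s = 1, six sites are unexamined. Three of the six would have to carry an unrecorded reaction, (1 + 3)/8 = 50%, before the SAP-rule figure matched the dosed population.

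**Later MAD doses.** The Day 36, 58 and 59 procedure lists contain no site check of their own, so only the persistence rule in 7.2.12 operates. If a site is examined only while it is reacting, the percentage is s/s = 100% at any visit with data.

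**The case against.** Several objections have weight.

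- **The SAD schedule.** The SAD Schedule of Activities row for site assessment carries three marks and no condition that a reaction must have occurred. Their column positions are not certain in the available text, but they fit Days 1, 2 and 5. If sites examine everyone on those days, the SAD distortion disappears. This stands, and it shows that the schedule and procedure text need reconciling. The MAD row cannot be read in the available text, so no inference is drawn from it.
- **Discretionary checks.** The protocol allows further examinations where judged necessary, which reduces the inflation, as shown by m above. This stands, but the denominator then depends on site practice.
- **Other displays.** SAP 10.2.2.6 does not promise percentages outright; they follow from the general rule, and the table shells are still to come. Counts and full listings would let a careful reader recognise 1/2 for what it is. That softens the effect but does not correct the percentage. Missing counts appear only where applicable and would label planned non-examination as missing. The rule that suppresses cells with more than half the data missing is written for PK only.

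Three stronger readings are tempting, and the documents do not support them.

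- **That the rate must rise after Day 1.** It rises only if s/k > k/n; the table has cases where it falls.
- **That it drifts to 100% as reactions resolve.** On SAD Days 2 and 5 and MAD Day 2 the trigger is a Day 1 reaction, not a persisting one, so resolved reactors are still examined and enter as zeros. The 100% result needs the stricter 7.2.12 reading.
- **That the same rule distorts SAD GGT and LDH**, which Table 9 restricts: "SAD Cohorts: will be performed in subjects with ALT and/or AST" at or above 3 times the upper limit of normal. A percentage denominator does not govern visit means or changes, and those are reported with n.

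**Conclusion.** The point holds in a limited form. If sites follow the procedure text, the site-reaction percentages after 2 hours are conditional on having reacted. They overstate the proportion of dosed subjects affected by about n/k whenever at least one reaction persists: roughly 2- to 8-fold in groups of 6 to 8, and 5- to 16-fold in the group of 16, for an assumed 1 to 3 reactors. They are not comparable with placebo or between doses.

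This rests on assumed reaction counts, on few non-reactors being examined, and on unexamined sites being mostly clear. A reader might infer that the primary safety results are compromised. They are not: the primary endpoints are adverse events and anti-drug antibodies, and site findings judged to be adverse events are counted by subject incidence, independently of these visit denominators. The 0 to 2 hour percentages are also sound.

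**What to change.** Add to SAP 10.2.2.6, in substance:

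> Percentages at the assessments from immediately to 2 hours after each dose use the subjects assessed. At later visits the denominator is all subjects in the group who received that dose and attended the visit. A site not re-examined because no reaction had been noted is counted as no reaction, as an explicit exception to SAP 9. The number of subjects actually examined is shown beside each percentage. Dose occasions are compared on the 0 to 2 hour data only.

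Separately, reconcile the SAD Schedule of Activities row with Protocol 6.2.4, 6.2.7 and 7.2.12, so that it is clear who is to be examined after Day 1.

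The cost is a few sentences in the SAP and a changed denominator in one table program, before the shells are written. No new data are needed. The small downside is that a late-onset reaction the subject does not report is counted as absent; showing the number examined makes that visible.

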10.2. Statistical Analyses

Data will be summarized in a descriptive manner. MMRM analysis with treatment, visit, and visit by treatment as fixed effects, subject as a random effect, and baseline value as covariate adopting unstructured covariance structure may be performed as indicated.

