The Schedule of Activities table in the study protocol provides an overview of the protocol visits and procedures. Refer to the Study Procedures and Assessments sections of the protocol for detailed information on each procedure and assessment required for compliance with the protocol.

Multiple-Dose Cohorts:

The multiple ascending dose (MAD) portion will be conducted in approximately 4 planned cohorts, 75 mg, 150 mg, 250 mg, and a fourth cohort with dosage and regimen to be determined based on the review of the safety data from the previous cohort(s), with a total of up to approximately 40 subjects (8 PF-06293620: 2 placebo per cohort).

Subjects and the site personnel in the MAD cohorts will be blinded to treatment and treatment regimen. The MAD cohorts will be run in parallel with the remaining SAD cohorts. Based on the ongoing review of the safety data of the previous SAD and MAD cohort(s) the order of initiation of the MAD cohorts may be adjusted but at no time will the dose exceed the PK exposure from the SAD portion. MAD safety data from the previous cohort(s) will be used to determine the dose and dose regimen of the fourth planned cohort. An additional fifth cohort may be studied to obtain further safety and PK data, increasing the planned total number of subjects to approximately 50. At no time will the MAD dose exceed PK exposure from the SAD. The MAD subjects will receive SC administration of study drug (PF-06293620 or placebo) every 4 weeks (on study Days 1, 29 and 57) in 3 of the originally planned 75 mg, 150 mg and 250 mg cohorts. However, after 150 mg/kg dose cohort, it was determined that it would be unnecessary to study doses higher than 150 mg/kg. A decision was made to study 50 mg/kg dose and to expand 75 mg/kg dose cohort for additional pharmacodynamics evaluations. The final study dose cohorts and number of subjects randomized are outlined in [Table 2](#).

Table 2. Final MAD Cohorts and Dosage Levels

Dose	Route	Frequency	Number of Subjects
50mg Placebo	SC	Q4weeks	8
			2
75mg Placebo	SC	Q4 weeks	16
			4
150mg Placebo	SC	Q4weeks	8
			2

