10.2.2.5. Ambulatory Blood Pressure Monitoring (ABPM)

For MAD portion of the study, ambulatroy blood pressure (ABP) reading will be acquired using the ABPM equipment provided by Biomedical Systems to evaluate potential treatment effect on ABP. Ambumlatory blood pressure are scheduled to be recorded at the following visits:

Table 7. ABPM Visit Schedule

Protocol Visit	Visit code to be selected
Day-2 / Day -1	Day -2
Day 1/ Day 2	Day 1
Day 7/ Day 8	Day 7
Day 63/ Day 64	Day 63
Day 84/ Day 85	Day 84
Unscheduled	UNS
Certification	CERT
Test	TEST

Summary of ABPM measures mSBP, mDBP, mHR, and mMAP represent weighted means of systolic blood pressure, diastolic blood pressure, heart rate and mean arterial pressure (MAP), respectively, and will be summarized in three time increments for a given measurement period: 24 Hour, Day Time (06:00 – 22:00), and Night Time (22:00 – 06:00). mXXX will be calculated using an area under the curve approach over the collection time interval, normalized by the time interval: $AUC(0-t) / t$. Mean over study days by treatment line plots will be produced along with spaghetti plots of individual profiles over study days grouped by treatment. The number and percentage of subjects with SBP > 140 mmHg, and DBP > 90 mmHg will be tabulated by treatment and Study Day, respectively. Additionally, mSBP, mDBP, mHR, and mMAP response will be modelled using a MMRM with corresponding baseline as covariate, and treatment and visit as fixed factors. Mean change from baseline over time with active treatment may be compared to the mean change from baseline over time with pooled placebo treated subjects using MMRM analysis with treatment, visit, and visit by treatment as fixed effects, subject as a random effect, and baseline value as covariate adopting unstructured covariance structure. For displaying purpose, Mean(\pm SE) of hourly average of absolute SBP, DBP, HR, MAP, and change from baseline will be plotted by Study Day and 24-hour time per treatment group; by treatment and 24-hour time per Study Day. Line plots of individual 20-min measurements of each subject will be plotted by study Day and time, and group by treatment and dose group. Least square means (\pm SE) of day Time, Night Time, and 24 Hour mSBP, mDBP, mHR, and mMAP will be plotted by treatment and Study Day. If warranted, a longitudinal Emax model may be developed to further characterize the potential treatment effect on ABPM.

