10.2.4. Pharmacodynamic Analyses

PD biomarker data will include fasting plasma glucose, fasting glucagon, fasting GLP-1, 24-hr glucose profile (finger-stick), mean daily glucose profile, HbA1c, fructosamine, 1,5-anhydroglucitol, and glucose, insulin, C-peptide, glucagon and GLP-1 AUC after mixed meal tolerance test (MMTT, 4 hr). The relationship between changes in the values of these biomarkers with the pharmacokinetics of PF-06293620 may be explored. Exploratory PK/PD modeling may be performed if visual examination of the data is suggestive of a relationship.

The change and percentage change from baseline for PD biomarkers over the period of the study will be tabulated by treatment. The mean change from baseline values over time per cohort will also be tabulated. Data will be presented in tabular and graphical format and summarized descriptively. Descriptive statistics on change from baseline in fasting plasma glucose, fasting glucagon, fasting GLP-1, 24-hr glucose profile (finger-stick), HbA1c, fructosamine, 1,5-anhydroglucitol, and glucose, insulin, C-peptide, glucagon and GLP-1 AUC after mixed meal tolerance test (MMTT, 4 hr), and lipid parameters will be provided separately for each treatment and the pooled placebo group. The mean change from baseline over time with active treatment may be compared to the mean change from baseline over time with pooled placebo treated subjects using MMRM analysis with treatment as fixed effect, subject as a random effect, and baseline value as covariate adopting unstructured covariance structure. Figures of absolute values, change from baseline, and percentage change from baseline over time may be produced if needed.

The relationship between changes in the values of these biomarkers with the pharmacokinetics of PF-06293620 will be explored. Exploratory PKPD modeling may be performed if visual examination of the data is suggestive of a relationship.

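### The SAP's MMRM pairs a redundant random subject effect with an unstructured covariance; for endpoints with many visits, the 10.2.4 form gives standard errors that are far too small

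*SAP*

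**What the plan says.** Three SAP sections describe the same optional model.

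- **10.2 (general):** treatment, visit and visit-by-treatment as fixed effects, with "subject as a random effect, and baseline value as covariate adopting unstructured covariance structure may be performed as indicated".
- **10.2.2.5 (ABPM):** the comparison with pooled placebo has the same fixed effects, again with "subject as a random effect, and baseline value as covariate adopting unstructured covariance structure". Just before this, the section commits to an MMRM for the weighted means of blood pressure and heart rate. That one has baseline, treatment and visit, and names no covariance structure and no random effect.
- **10.2.4 (PD biomarkers, including fasting glucose):** active may be compared with placebo "using MMRM analysis with treatment as fixed effect, subject as a random effect, and baseline value as covariate adopting unstructured covariance structure". Neither visit nor visit-by-treatment is listed.

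SAP 10.1 states that "Placebo subjects will be pooled across cohorts for analysis and presentation purpose" and allows 90% confidence intervals for PD endpoints. SAP 9 rules out imputation. For the MMRM, the SAP gives no list of visits, no degrees-of-freedom method, no convergence rule and no fallback structure.

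**The concern.** An unstructured covariance leaves every variance and covariance free. A random subject intercept adds one constant to every entry of that matrix, so the data cannot separate the two components. Depending on the software, the result is a warning, a dropped term or a failure to converge. The SAP does not say what happens next, and the sponsor is unblinded.

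The second issue is more important because it remains when the fit converges. If a single treatment effect is assumed across many visits, the estimated unstructured matrix decides how the visits are weighted. With 20 visits and 40 subjects those weights are very noisy. The ordinary model-based standard error treats them as known, so the reported error bars for active against placebo on fasting glucose would be too short. That is the kind of result likely to feed later dose selection.

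**Working it through.** **Inputs**

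- *Subjects:* SAP Table 2, "Final MAD Cohorts and Dosage Levels", gives (8+2) + (16+4) + (8+2) = 40, of whom 32 are active and 8 placebo. This agrees with the planned total of about 40. With placebo pooled there are 4 groups.
- *MAD fasting glucose visits:* Protocol 6.3.5 to 6.3.29, with Day 1 pre-dose as baseline (SAP Table 3). The days are 2, 3, 8, 15, 28, 29, 36, 43, 57, 58, 59, 64, 71, 78, 84, 85, 99, 113, 141 and 169, so T = 20. Days 8 and 64 are the time-0 samples of the meal test. SAP Appendix 1 has a window for each of the 20.
- *SAD fasting glucose:* Protocol 6.2 gives Days 2, 3, 4, 5, 8, 15, 22, 29, 43, 57 and 85, so T = 11, with 40 planned subjects in 6 groups.
- *ABPM:* post-baseline Days 1, 7, 63 and 84, so T = 4.

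**Step 1: redundancy.** The total covariance is V = s²J + U, where J is all ones and U is unstructured. Replacing (s², U) by (s² + c, U − cJ) leaves V and the likelihood unchanged. At T = 20 there are 210 + 1 = 211 parameters and the Jacobian has rank 210. At T = 4 there are 11 parameters and rank 10. The excess is exactly one at any sample size.

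**Step 2: parameter counts, T(T+1)/2.**

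| Endpoint | T | Covariance parameters |
|---|---|---|
| MAD fasting glucose | 20 | 20×21/2 = 210 |
| same, through Day 85 | 16 | 136 |
| MAD fasting glucagon | 14 | 105 |
| SAD fasting glucose | 11 | 66 |
| MAD HbA1c | 6 | 21 |
| ABPM | 4 | 10 |

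**Step 3: can the unstructured matrix be fitted alone?** Yes, with complete data. Residual df are 40 − 4 − 1 = 35, against 20 visits. In 2000 simulated datasets (assumed covariance) the estimate was always positive definite, but it was poorly determined: median condition number 1033 against a true 137. As an illustration with missing visits, 24 completers taken alone leave 24 − 5 = 19 df for 20 visits.

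**Step 4: error bars under the 10.2.4 model.** Two simulations used a treatment effect common to all visits, complete data and an assumed covariance.

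- First, at 20 visits: mean model-based SE 7.9 against an empirical SD of 18.2 (ratio 2.30). Nominal 90% coverage was about 52% at 20 visits, 76% at 11 SAD-type visits and 89% at 4 visits.
- Second, with free visit means and 36 df: SE 7.4 against 16.8 (ratio 2.27). Coverage was about 55% at 20 visits and 88% at 4.

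A closed form for complete normal data confirms the size. With ν residual df, the true variance of the estimate divided by the expected model-based variance is

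[(ν − 1)/(ν − T)] × [ν/(ν − T + 1)].

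Approximate coverage is then 2Φ(t/√ratio) − 1, where t is the 95th percentile on ν df.

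| Case | ν | T | Variance ratio | √ratio | Approx. coverage |
|---|---|---|---|---|---|
| MAD fasting glucose | 35 | 20 | (34/15)(35/16) = 4.96 | 2.23 | 2Φ(1.690/2.23) − 1 ≈ 55% |
| SAD fasting glucose | 40 − 6 − 1 = 33 | 11 | (32/22)(33/23) = 2.09 | 1.44 | 2Φ(1.692/1.44) − 1 ≈ 76% |
| 4 visits | 35 | 4 | (34/31)(35/32) = 1.20 | 1.10 | 2Φ(1.690/1.10) − 1 ≈ 88% |

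The ratio does not involve the covariance itself, so the shortfall does not hinge on the covariance that was simulated. Visit main effects without the interaction leave it unchanged, because the treatment effect is still common across visits.

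**Step 5: error bars under the 10.2 model.** With visit-by-treatment terms and complete data, each visit's contrast is essentially a comparison of group means at that visit. Simulated per-visit coverage is about 90%.

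**The case against.** The strongest reply is that this is a wording slip in an optional analysis. The term MMRM suggests that the subject was meant as the unit of repeated measurement. Software that drops the redundant term returns the ordinary unstructured fit with the same contrasts. The study is exploratory with no hypothesis tests (SAP 6.1), the model is permitted and not required, and SAP 2 requires unplanned analyses to be identified in the report. Much of this stands and limits the importance of the point.

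Three stronger readings are tempting but not supported.

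- *The model cannot be estimated and the software will stop.* Only the split between the two components is unidentified. V and the contrasts are identifiable, and behaviour depends on the software.
- *210 parameters for 40 subjects rules out an unstructured fit.* Step 3 shows that it can be fitted with complete data. The 210 also assumes that all scheduled visits enter, which Appendix 1 supports but no MMRM sentence states.
- *This is the only comparison of active with placebo.* SAP 10.2.2.5 has a committed ABPM model without this wording and mentions a possible Emax model. SAP 10.2.4 and Protocol 9.6 provide descriptive summaries by dose and for pooled placebo, and Protocol 9.6 also compares active with placebo.

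What the reply does not answer is Step 4. Dropping the redundant term leaves the standard errors under 10.2.4 just as short.

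**Conclusion.** The point holds in two parts. The random subject effect is redundant in all three sections, which is a drafting fault with limited consequences. The more serious fault is the unstructured covariance combined with the 10.2.4 fixed effects for endpoints with many visits. For MAD fasting glucose, standard errors would be less than half of what they should be, and nominal 90% intervals would cover about 52% to 55%. For SAD fasting glucose coverage would be about 76%. At 4 visits the loss is small (88% to 89%).

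These figures assume complete, normally distributed data, a treatment effect common to all visits, all scheduled visits in the model, all 40 subjects analysed, and ordinary model-based standard errors. They do not apply to per-visit contrasts from the 10.2 model, which are close to nominal with complete data. Because the analysis is exploratory and optional, the SAP should be corrected, but nothing in the primary safety objective depends on it.

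**What to change.** In SAP 10.2, 10.2.2.5 and 10.2.4:

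1. Delete the random subject effect wherever unstructured covariance is used.
2. Use the fixed effects of 10.2 (treatment, visit, visit-by-treatment, with baseline as covariate) in 10.2.4 as well.
3. State Kenward-Roger standard errors and degrees of freedom.
4. Keep unstructured covariance for endpoints with few visits, such as ABPM with 4.
5. For endpoints with many visits, list the visits that enter and pre-specify a structure suited to unequal spacing, as the primary or fallback choice. One option is spatial power on study day plus a random subject intercept, where the intercept is not redundant. Toeplitz or AR(1) by visit order suits this schedule poorly, because gaps run from 1 day (28 to 29, 57 to 58) to 28 days (113 to 141, 141 to 169).

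The cost is a few sentences in three sections before database lock, with no change to data, sample size or conduct. The statistical downside is small: slightly wider intervals and some reliance on the assumed structure.
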